- i. Changes in Cardiorespiratory fitness (VO₂peak): Subjects will be tested for VO₂peak at baseline and post training using a Bruce protocol on a treadmill as previously performed (13, 97). Relative (ml/kg-1/min-1) and absolute (L/min-1) VO₂peak and treadmill time to exhaustion will be used as determinants of fitness while additional measures of respiratory quotient (RQ) and heart rate at each stage of the GXT, and heart rate recovery and excess post oxygen consumption following the test will also be measured as determinants of exercise training adaptations. Blood CK levels will be assessed 30 minutes following the cessation of exercise and also 24 hour later. In addition, sub-maximal exercise (60% HRR) measures of heart rate, RQ, and O₂ consumption will also be determined during exercise training sessions occurring during the first week and the last week of training.

b. Secondary Objectives:

- i. Mitochondrial Responses in Skeletal Muscle: Multiple aspects of mitochondrial function (basal and ADP-stimulated respiratory kinetics under multiple substrate combinations, H₂O₂ production and emitting potential) will be assessed in duplicate on permeabilized fiber bundles from freshly obtained muscle biopsy samples as previously described (61-64). Fibers are then freeze dried for determination of citrate synthase activity (index of mitochondrial content). Frozen muscle tissue will also be analyzed for electron transport complex activity, content (Western blot using complex I through V antibody cocktail) and cellular redox state (GSH/GSSG, thioredoxinred/thioredoxinox) as previously described (63). Of the remaining approximate ≥ 90 mg of muscle biopsy tissue, a small portion (<5

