B. Study Type and Design: This study is a longitudinal, repeated measures, double-blinded design with subjects randomly assigned to placebo, low (20 mg/d) or high (80 mg/d) atorvastatin therapy during a 12-week aerobic exercise training protocol. We expect to screen approximately 150 participants to enroll (randomize) a maximum of 80 participants. The overall goal is to have 60 participants complete all study procedures (20 in each group). Repeated measures design allows each subject to serve as their own control. Placebo groups are included to account for potential changes in muscle mitochondrial function independent of statin therapy over the 1 year dose-response.

C. Sample size, statistical methods, and power calculation: The randomization for study drugs will be carried out by the biostatistician using a computer-based random number generator at a 1:1:1 allocation. Sample size for the study is powered on the basis of detecting a difference in VO₂peak between the EX+Plac group and the EX+Atorva80 group as well as between the EX+Atorva20 group and the EX+Atorva80 group at 12 weeks post-treatment. In our previously published study(13) (Table 2) the EX only group had a mean 2.6 ml/kg/min increase in VO₂peak following 12 weeks of training while the EX+Statin group only had a 0.4 ml/kg/min increase in VO₂peak. The estimated effect size of between group differences is 0.9 (Cohen's d). The increase of VO₂peak in the EX+Atorva20 group is expected

to be similar to that of EX+Plac group. A sample size of 35 per group provides 80% of power of detecting an effect size of 0.75 for a two-sided, two-sample t-test at 0.025 levels. Here, we use 0.025 for each group comparison to maintain the overall type I error rate at 0.05 level using Bonferroni correction. Assuming variances similar to what was observed in the pilot study, this study is powered to detect a difference of 1.53 ml/kg/min VO₂peak between groups. These power calculations led to a desired final sample size of 105 (35/group). We plan an enrollment of 120 (40/group) subjects to account for 10% dropout rate. The subject enrollment will be split equally between the two sites. As an exploratory analysis, the mean difference of VO₂peak (EX+ Atorva20- EX+ placebo) and its 95% confidence interval (CI) will be estimated. If the lower bound of the 95% confidence interval is greater than -0.8 ml/kg/min, EX+ Atorva20 will be considered non-inferior to EX+ placebo.

D. Subject Criteria

[figure not shown]

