- iv. Muscle biopsy: After an overnight fast, the participant will complete a survey to confirm the absence of bleeding disorders, and avoidance of NSAIDs and aspirins for 7 days prior to biopsy. Participants will then lie on a table in a supine position. A location on the mid-thigh will be identified. The area will be properly shaved and then thoroughly cleaned using sterile techniques (alcohol and iodine). A sterile drape is then placed over the leg with the biopsy site showing through a fenestration in the center of the drape. A numbing agent will be lightly sprayed onto the biopsy location (ethyl chloride) immediately before the skin, adipose, and muscle fascia is anesthetized with lidocaine (1-2% HCL). After allowing 1-2 minutes for the site to become numb the skin and fascia is incised with a sterile scalpel (#11). The Bergstrom needle (5mm) is then placed through the incision into the vastus lateralis muscle. Suction is applied to the proximal port of the needle, and the tissue is cut rapidly with the internal portion of the needle, and the entire needle is removed from the incision. Sterile gauze is placed on the incision site and pressure is applied with an ice pack for ~5 minutes. The site is then closed with a steri-strip and band-aid. Sterile gauze is then applied on top of the band-aid and pressure is applied by wrapping coban around the thigh. Approximately 100-200 mg of skeletal muscle will be collected during each biopsy in one pass. In the case where less muscle is harvested per pass, one more additional pass will be taken with the participants consent. The tissue collected is

dissected free of connective tissue and separated for mitochondrial function studies or frozen in liquid nitrogen for subsequent biochemical analyses as done previously (13, 61). After analysis for current project is complete any remaining muscle samples will be stored indefinitely for future research. Muscle biopsies will be repeated at 4 weeks and 12 weeks. [name] has performed over 300 skeletal muscle biopsies without incidence since starting his independent lab in 2005. See appendix for letter from IRB Director ([name]) at [name] previous institution (MU) stating his record for conducting muscle biopsies and a letter of support for the procedure from [name], the Director of the CTSU. Additionally, Neurologists who study various muscle diseases regularly perform the technique at KUMC. Muscle biopsies will be repeated at 4 and 12 weeks.

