- E. Quality Assurance / Monitoring:** Data will be reviewed twice a year by the Board Chair. In addition, data will be reviewed on a yearly basis with the biostatistician, [name] to determine if the studies should be shortened due to either no measured effect or due to effects that are greater than what power calculations indicated. The PI and other key personnel will be examining research data on a subject to subject basis to ensure it is accurate and to address any potential problems that may arise with the protocols. In addition, Drs. [name] and [name] will discuss data at least once per month through in person meetings or by phone to ensure that data collection is occurring in a consistent manner at both locations.

V. Data Analysis and Reporting

- A. Statistical and Data Analysis:** This project is a two-factor study. One factor is treatment group (between subjects) and a second factor is time of data collection (0, 1, 6, and 12 months) (within subject). The data analysis will be carried out for the primary outcome variable of cardiorespiratory fitness, in addition to other outcome variables (muscle mitochondrial change, and insulin sensitivity, etc.). For each measure, its baseline measure and age will be added as covariates to adjust for the individual difference at baseline. Two-way interaction between treatment and time will be added in the model for testing if the outcome changes differently between groups over time. Additional variables, such as demographics, BMI, physical activity, etc. may also be included as covariates. If the test of trend difference is significant, then the comparison at each time point will also be considered to identify when the difference between groups reaches the maximum. Least Square Means will be used for the aforementioned comparisons. The statistical analysis will be performed with mixed procedure in STATA 13.1 (StataCorp LP, College Station, TX). Mixed model does

not require complete data for a longitudinal study. Residual analyses will be conducted and efforts to address those will be made, including appropriate transformations.

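### V.A makes visit-level arm comparisons follow a significant treatment-by-time test, II.C powers week-12 comparisons without that condition, and the cost depends on how baseline is coded

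*Combined protocol and SAP*

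**What the plan says.** Section V.A (Statistical and Data Analysis) plans a mixed model with arm and time as factors: "Two-way interaction between treatment and time will be added in the model for testing if the outcome changes differently between groups over time". The next step is conditional: "If the test of trend difference is significant, then the comparison at each time point will also be considered". Its stated purpose is "to identify when the difference between groups reaches the maximum". V.A spells out no other contrast between arms and gives no significance level for the preliminary test.

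V.A gives baseline two roles. It is an adjustment variable: "For each measure, its baseline measure and age will be added as covariates". It also appears among the levels of time: "a second factor is time of data collection (0, 1, 6, and 12 months) (within subject". The month values do not fit a 12-week trial. The point below stands once they are read as weeks 4 and 12.

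Section II.C takes a different route for VO2peak. It names two pairwise comparisons at 12 weeks, sizes them by a two-sample t-test, and sets the error rate: "Here, we use 0.025 for each group comparison to maintain the overall type I error rate at 0.05 level using Bonferroni correction". It mentions no preliminary test.

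The visits differ by outcome:
- VO2peak (II.A, primary objective): "Subjects will be tested for VO₂peak at baseline and post training". II.E.a.x agrees, with one repeat at week 12.
- Muscle biopsy (II.E.a.iv): "Muscle biopsies will be repeated at 4 and 12 weeks".
- Fasting blood (II.E.a.iii): weeks 4 and 12.
- IVGTT (II.E.a.iii) and NIRS (II.E.a.v): week 12 only after baseline.

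**The concern.** A treatment-by-time test asks whether the arm difference changes between visits. It does not ask whether there is a difference at week 12. If baseline is only a covariate, the responses for biopsy and fasting-blood outcomes are the week-4 and week-12 values. An arm difference that is fully present at week 4 and unchanged at week 12 then produces no interaction. Taken literally, V.A offers no visit-level comparison in that case, even for a large difference.

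For outcomes with one post-baseline visit, the same coding leaves no interaction to test, so the condition is undefined. That group includes the primary outcome.

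What is at stake is whether the two contrasts the trial was sized for, and their counterparts on the mechanistic outcomes, are reported as planned estimates. As written, that depends on a preliminary test whose behaviour rests on a coding choice the plan leaves open.

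**Working it through.** **Inputs.** From II.C: 35 per arm, effect size d = 0.75, two-sided 0.025 per comparison, 1:1:1 allocation, and 20 mg expected to behave like placebo, so the arm pattern is (0, 0, −d). Assumed, because V.A does not give them: preliminary test at 0.05, equal correlation between visits, complete data. The d of 0.75 is the VO2peak planning value and serves only as an illustrative size for other outcomes.

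**1. Reproduce II.C.** By the normal approximation, n = 2(z₀.₉₈₇₅ + z₀.₈₀)²/0.75² = 33.8, so 34 per arm. By the noncentral t at n = 35, the noncentrality is 0.75 × √(35/2) = 3.14 and power is 79.9%. The plan's 35 per arm and 80% are confirmed, for a comparison made without a preliminary test.

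**2. Baseline as covariate only, two response visits.** With three arms, the interaction test is a one-way analysis of variance on (week 12 − week 4), with F on 2 and 102 degrees of freedom. Let the residual SD be 1 at each visit and ρ the correlation between visits. The difference has variance 2(1 − ρ). If the 80 mg arm shifts by Δ between week 4 and week 12, the noncentrality is λ = 35 × (2/3)Δ² / [2(1 − ρ)].
- Effect complete by week 4 and held: Δ = 0, so λ = 0. The test is significant at its null rate, 5%, whatever d is.
- Half the effect at week 4: Δ = 0.375. For ρ = 0.3, 0.5, 0.7, λ = 2.34, 3.28, 5.47, and the test is significant in about 25%, 34% and 53% of trials. Simulation gave 25%, 34% and 54%.

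**3. VO2peak with time 0 kept as a response.** The interaction is the 2-df test of difference in change, with λ = 35 × (2/3) × 0.75² = 13.1. It is significant in about 90% of trials.

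**4. Simulated power for placebo versus 80 mg at week 12** (8,000 trials, 35 per arm, SD of change 1). Without the condition, power is 79.6 to 79.7%.

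| Coding | Effect present at week 4 | Preliminary test significant | Power with the condition |
|---|---|---|---|
| Covariate only; weeks 4, 12 | all | 5.2% | 3.7% |
| Covariate only; weeks 4, 12 | half | 33.6% | 30.4% |
| Covariate only; weeks 4, 12 | none | 90.5% | 74.2% |
| Time 0 a response; 0, 4, 12 | all | 92.6% | 78.0% |
| Time 0 a response; 0, 4, 12 | half | 81.8% | 73.7% |
| VO2peak, time 0 a response; 0, 12 | not measured | 89.9% | 78.7% |

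If 20 mg lies halfway between placebo and 80 mg, the VO2peak figure falls from about 80% to about 77%.

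**5. VO2peak, IVGTT and NIRS with baseline as covariate only.** One response visit remains. Arm and arm-by-time cannot be separated, so the preliminary test does not exist.

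**6. Smaller size.** II.B aims for 20 completers per arm. At that size, with the effect held from week 4, power without the condition is 52.0%. With it, power is 2.6% (covariate only) or 46.5% (time 0 a response), and 49.8% for VO2peak with time 0 a response.

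**The case against.** Much of the case on the other side stands.

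- A reader might infer that an early, steady effect is certain to be missed. The documents do not settle that. V.A lists time 0 as a level, and if baseline is a response, a profile of zero, then d, then d is itself an interaction, which the test detects about 93% of the time.
- A reader might infer that V.A never compares the arms unless the interaction is significant. The sentence does not say that comparisons are made only in that case, and it can be read as a follow-up on timing. Arm is also a factor in the model, so a steady effect could appear as a main effect. V.A neither specifies nor excludes that test.
- A reader might infer that the primary comparisons face two hurdles. They do not: the Bonferroni split in II.C divides alpha and is not a precondition. V.A also nowhere says that the II.C comparisons are withheld when the interaction is null.
- A reader might infer that the visit with the largest difference becomes the reported result. V.A says only that its timing will be identified, and VO2peak has a single post-baseline visit.
- The 5% figure is an extreme case. Section V.B expects mitochondrial improvement to follow transcription-factor changes at 1 month, and the Background describes statin effects on muscle as possibly progressive. A growing effect is therefore the more natural expectation for those outcomes.
- The condition also acts as an informal restraint on many secondary outcomes.

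None of this reconciles V.A with II.C or says which coding applies.

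**Conclusion.** The point holds as a fault of specification. V.A attaches a condition to the visit-level comparisons, II.C powers week-12 comparisons without one, and V.A leaves open the coding that decides whether the condition matters.

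With baseline as a covariate only, biopsy and fasting-blood outcomes are exposed. In the illustration, power falls from about 80% to about 4% when the effect is complete by week 4, and the preliminary test is passed in only about 25 to 55% of trials when half the effect is present then. VO2peak, IVGTT and NIRS then have no interaction to test. With time 0 kept as a response, the loss is about 1 to 6 points, and about 1 to 3 for VO2peak.

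The primary outcome's power is therefore not seriously threatened under either coding. Its problem is that V.A does not describe the comparison that II.C powers. The figures rest on an assumed 0.05 level for the preliminary test, equal correlations, complete data, and an effect size borrowed from VO2peak.

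**What to change.** Amend V.A as follows:
1. Placebo versus 80 mg and 20 mg versus 80 mg at week 12 are estimated from the model with confidence intervals, whatever the interaction test shows. VO2peak is tested at 0.025 for each comparison, as in II.C. Other outcomes are labelled secondary, without alpha control.
2. Baseline is a covariate and not also a response. Time levels follow the visits of each outcome: weeks 4 and 12 for biopsy and fasting blood, week 12 alone for VO2peak, IVGTT and NIRS. For the single-visit outcomes, the model becomes an analysis of covariance.
3. Week 12 is the main visit, and week 4 is supportive.
4. The treatment-by-time test and the timing of the largest difference are descriptive only.

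The cost is wording: no added data, and the VO2peak alpha in II.C is unchanged. The downside is that secondary outcomes lose the informal restraint of the condition, so their p-values should be labelled as not adjusted for multiplicity.

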mg) will be prepped for electron microscopy for future analysis of morphology (mitochondrial size, content, ragged muscle fiber analysis) (66). Remaining muscle will be frozen for later analysis of intracellular atorvastatin concentration (both the acid and lactone forms) (67), ubiquinone (co-enzyme Q10) (68, 69), and potential future gene array, metabolomics, or proteomics analysis. An in-vivo assessment of mitochondrial function using NIRS will determine muscle oxygen consumption (mVO₂) and the recovery kinetics will be determined during a series of repeated arterial occlusions following maximal knee extension. The mVO₂ data are fit to a mono-exponential function to calculate the rate constant, which is directly related to the mitochondrial respiratory capacity. (46). The protein and mRNA for key transcriptional factors controlling mitochondrial biogenesis and function will also be measured (PGC-1 α , NRF-1, NRF-2, mTFA) in all subjects as done previously (98, 99). In addition, muscle will be frozen in OCT to examine if there are altered fiber type changes, and or other important markers including apoptosis (TUNEL staining).

- ii. Body Composition, Physical Function, Pain Assessments, and Physical Activity: DEXA will measure bone mineral content (BMC), bone mineral density (BMD) and body composition (fat mass, fat-free mass, and percent body fat). Pressure thresholds will be determined using an algometer during rest and after exercise. Current and usual whole body muscle pain while resting using 0-10 numeric scale. Steps, physical activity and sedentary time will be determined over a 5-day period using pedometers and accelerometers. (BodyMedia Sensewear).
- iii. Fasting Blood Draw: Glucose, insulin, total cholesterol, HDL-C, LDL-C, and triglycerides, CK, creatinine and ALT will be measured in fasting blood samples.
- iv. Insulin Sensitivity: Glucose and insulin, and insulin sensitivity will be calculated using a minimal model program following the IVGTT.
- v. Cardiovascular Function: Heart rate ECG will be measured under resting and maximal exercise conditions.

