a. Inclusion criteria/Exclusion criteria:

- i. Inclusion Criteria
 - Ages 35–60 years
 - BMI between 30-39 kg·m²
 - Sedentary (less than 30 min of physical activity/week during last 6 months)
 - Weight stable (no more than 5% change in body weight the previous 3 months)
 - >5% risk for a cardiovascular event in the next 10 years according to the 2013 American College of Cardiology/American Heart Association risk calculator and/or 2 out of 5 metabolic syndrome risk factors (Triglycerides \geq 150 mg/dL; HDL \leq 40 mg/dL; Glucose \geq 100 mg/dL; Waist Circumference \geq 102 cm for males, 88 cm for females; Blood pressure: \geq 130 mmHg systolic and/or 85 mmHg diastolic or being treated for hypertension).
 - Stable doses of medications for 90 days
 - Willing to stop all NSAIDs and aspirin for 7 days prior to muscle biopsy
 -
- ii. Exclusion Criteria
 - Smoking
 - Previous use of statins
 - Use of other medications or supplements that affect lipid profiles or body weight in the last 6 months
 - e.g., fibric acids, bile acid sequestrants, nicotinic acids, fish oil
 - Diagnosis of chronic diseases including CVD, diabetes, other metabolic diseases (e.g., thyroid), cancer, HIV, or acquired immunodeficiency syndrome
 - History of abnormal bleeding problems
 - Currently taking (within the last 10 days) anti-platelet medication (Plavix), Warfarin, and other anti-coagulants (eliquis, pradaxa, and xarelto) medications.
 - >2 fold upper normal limit (UNL) for ALT or creatinine
 - Women who are pregnant or breastfeeding
 - Individuals with polymorphisms (SLCO1B1) known to be associated with susceptibility for statin induced myopathies (tested at screening)
 - Currently enrolled in another research study

b. Withdrawal/Termination criteria: Subjects are free to abstain from taking their statins and leave the study at any time. We will test both muscle enzymes (creatinine kinase) and liver enzymes (ALT) to determine if statins are causing either muscle myopathies or liver injury. This testing will occur at baseline and at 1 month into taking statins. If enzymes are elevated, the subject will be taken out of the study for their own health.

E. Specific methods and techniques

This study will require approximately 13 total study visits plus exercising 5 times per week. The total time commitment of study visits is approximately 30 hours over the 12 weeks of study participation.

a. Testing Procedure

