- v. **Near InfraRed Spectroscopy (NIRS):** Muscle mitochondrial functional capacity will be measured non-invasively using a NIRS technique developed by [name], a member of the research team at ECU (46). Participants will perform submaximal knee extension exercise to increase muscle oxygen consumption (mVO_2) and the recovery kinetics is determined during a series of repeated arterial occlusions. The mVO_2 data are fit to a mono-exponential function to calculate the rate constant, which is directly related to the mitochondrial respiratory capacity. NIRS will be repeated at week 12.
- vi. **Pain Assessment:** Pressure pain threshold will be objectively assessed by a computerized algometer at rest and after exercise (73). In addition, we will ask participants to rate their current and usual whole body muscle pain while resting and moving using 0-10 numeric scales (0 = no pain, 10 = most intense pain imaginable) at different time points. We will ask the participants to rate the highest pain felt immediately and for up to 30 minutes after each maximal exercise test, as well as 24 hours later. Pain assessments will be repeated at week 12.
- vii. **Muscular Strength Assessment:** Knee isometric strength will be assessed using a Biodex dynamometer. Participants will be seated in a specialized chair and leg will be strapped to the dynamometer arm. Participants will also be secured to the chair to ensure isolation of the knee joint. Trained staff will instruct participants on how to gradually develop force in one second. Following 3 practice trials of submaximal contraction of both flexion and extension, participants will be asked to alternate between maximal flexion and extension with 60 seconds rest between contractions. There will be 3 trials of flexions and extension on both legs. Muscular strength assessments will be repeated at 1, 6, and 12 months
- viii. **Physical Performance Assessment:** A series of physical performance measurements will be performed to access balance, gait speed, and strength (74). The physical performance will be repeated at week 12.
- ix. **Body Composition:** Participants will be evaluated with dual energy x-ray absorptiometry (DEXA, Lunar Prodigy, version 11.2068, Madison, WI) to determine fat-free mass, fat mass and percent body fat at. DEXA uses very low X-ray doses (0.02mREM) to detect changes in body composition. DEXA body composition will be repeated at week 12.

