statin induced complications go away very quickly after stopping the therapy. Subjects who are discontinued from the study for a medical reason judged to be appropriate by the study doctors will receive the same reimbursement as if they completed the study to avoid the possibility that a subject would "soldier on" simply for the reimbursement.

- iii. **Muscle Biopsies:** Acute issues of muscle tightness, soreness, and bruising can be associated with muscle biopsies. More severe problems include the risk of infection. To avoid these issues the biopsy procedures are conducted with sterile techniques under medical supervision. Moreover, the subjects are given detailed instructions including how to take care of the incision site and who to contact should anything seem abnormal.
- iv. **IVGTT Catheter Placement and Venipuncture:** Their risk is very minimal. However, certain risks including discomfort, blood clot, minor bleeding, bruising, infection, and redness can occur. Aseptic techniques will be used to minimize such risks. Risks of bruising and minor pain can occur with venous phlebotomy. Venous catheter placements can rarely cause bleeding, bruising, soreness, and infection. Risk of bleeding after removal of the line also is possible. Infusion of glucose or insulin may cause the subject to feel nauseous or flushed. Drinks and snacks will be available for the subjects at the completion of the IVGTT should they have low blood sugar or feel nauseous.
- v. **DEXA:** The DEXA scan may make participants slightly uncomfortable because you have to hold very still. This research study involves exposure to radiation equal to approximately the level of radiation that most Americans receive in about 2 days from background radiation, such as naturally occurring radioactivity in the soil and air. The risk from radiation exposures of this magnitude is too small to be measured directly and is considered to be very low when compared with other everyday risks.

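### Pain has one dated follow-up rating, at week 12, so participants who leave earlier with muscle symptoms drop out of the comparison; a week-4 and exit rating plus a by-arm muscle-event table would be a cheap, optional improvement

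*Combined protocol and SAP*

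**What the plan says.** Pain is listed in II.A.b.ii under "Body Composition, Physical Function, Pain Assessments, and Physical Activity". II.E.a.vi says that the 0-10 muscle-pain ratings are taken "at different time points", without defining these, and then gives one date: "Pain assessments will be repeated at week 12". The ratings tied to maximal exercise tests add no intermediate date, because II.E.a.x repeats that test only at week 12.

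V.A does not name pain. It covers VO2peak and an open list of other outcomes, and its time points (0, 1, 6 and 12 months) do not match a 12-week study. Its modelling rule is general: "For each measure, its baseline measure and age will be added as covariates". On missing data it says only that a mixed model does "not require complete data for a longitudinal study".

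The plan provides for early exit. II.D.b states "Subjects are free to abstain from taking their statins and leave the study at any time" and, for muscle and liver enzymes tested at 1 month, "If enzymes are elevated, the subject will be taken out of the study for their own health". II.F.a.ii adds "Subjects who are discontinued from the study for a medical reason judged to be appropriate by the study doctors will receive the same reimbursement" as completers, so that nobody stays on for the money.

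Under II.K, staff assess adverse events at each testing visit and in scheduled telephone calls with everyone randomised. Slight expected soreness that does not alter the intervention is not counted. V.A lists no by-arm table of these events. V.B predicts that exercise with 80 mg will trigger pain.

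**The concern.** A mixed model tolerates incomplete data by using the post-baseline rows a participant does have. With a single post-baseline rating and baseline entered as a covariate, someone who leaves before week 12 has no such row. The model then estimates the pain difference among those who reached week 12.

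The people most likely to leave over muscle symptoms are those the pain measure is meant to detect, and V.B expects more of them on 80 mg. A small week-12 difference could therefore partly reflect who remained to be rated. V.B intends the results to inform the dose physicians choose for patients who exercise, so the pain result may be read as evidence on tolerability. A rating not taken at exit cannot be recovered later.

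**Working it through.** The plan gives no figure for pain, so there is none to reproduce. Its one design calculation, for VO2peak (II.C: effect size 0.75, two-sided 0.025, 80% power), does reproduce: 34 per group by the normal approximation, and 79.9% power at the stated 35 by the t-test. It does not bear on this point.

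**Inputs**
- p = 0.15, affected on 80 mg: from II.F.a.ii, which cites another trial.
- q = 0.05, affected on placebo: assumed; range 0 to 0.10.
- D = 3 points, higher rating in those affected: assumed; range 2 to 5.
- f, share of affected participants who leave before week 12: not in the documents; shown at 0, 25%, 50% and 67%.

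**Affected share among those rated at week 12** = p(1 − f)/(1 − pf), and the same with q. **Expected week-12 difference** = D × (80 mg share − placebo share).

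| f (both arms) | 80 mg share | Placebo share | Difference (points) | Shrinkage |
|---|---|---|---|---|
| 0 | 0.150 | 0.050 | 0.30 | 0 |
| 25% | 0.117 | 0.038 | 0.24 | 21% |
| 50% | 0.081 | 0.026 | 0.17 | 45% |
| 67% | 0.056 | 0.017 | 0.11 | 62% |

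For example, at 50%: 0.075/0.925 = 0.081; 0.025/0.975 = 0.026; 3 × 0.0554 = 0.17. Equal exit rates among those affected still shrink the difference. If only affected participants on 80 mg leave, it is 0.20, 0.09 and 0.02 at 25%, 50% and 67%.

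**Sensitivity to assumptions.** With D = 2, 0.20 falls to 0.16, 0.11 and 0.08; with D = 5, 0.50 falls to 0.39, 0.28 and 0.19. With q = 0 the full difference is 0.45, and 0.24 at f = 50%; with q = 0.10 it is 0.15, and 0.085.

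**Would a week-4 rating help?** A simulation assumed a baseline slope of 0.5, residual SD 1, and a week-4 to week-12 residual correlation of 0.5. The week-12-only model gave 0.24, 0.17 and 0.11 at f = 25%, 50% and 67%. Adding a week-4 row gave 0.28, 0.25 and 0.23 when symptoms were present by week 4. It recovered nothing when they began later (0.24, 0.17, 0.11). An exit-day rating is therefore useful as well.

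**How large could f be?** With 40 per arm and 10% dropout (II.C), 4 leave against 0.15 × 40 = 6 expected affected on 80 mg, so f is at most 4/6 = 67%. With at most 80 randomised and 60 completing (II.B), about 20/3 = 6.7 per arm may leave against 0.15 × 26.7 = 4.0 affected, so there is no cap. The low end is more plausible: people leave for other reasons, SLCO1B1 carriers are excluded (II.D.a), and the group's earlier simvastatin trial reported no myopathies (I.C). The enzyme rule alone removes few: 1% to 3.3% of 40 is 0.4 to 1.3 people, using the rates in II.F.a.ii, although this trial states no threshold.

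**What a by-arm event table can show.** At 15% against 5%, two-sided Fisher power at 0.05 is 18% with 40 per arm and 7% with 27. If only half of symptoms met the adverse-event definition (7.5% against 2.5%, assumed), it is about 3% with 40. A result of 6/40 against 2/40 gives a 10-point difference, exact 95% CI about −4 to 25. The table is descriptive.

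**The case against.** The premise is conditional. V.A does not name pain, and the undefined time points in II.E.a.vi, together with the 1-month point in V.A, could mean that a rating near week 4 is intended. If so, much of the loss is recovered when symptoms appear early. This stands as a reason for caution, but no such rating is dated.

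The exit rate, placebo rate and size of rise are assumed. Even with full retention the contrast is hard to detect: with 36 per arm and SD 1.5 (assumed), the standard error is 1.5 × √(2/36) = 0.35. Power is then about 13% at 0.30 and 10% at 0.24 (24% and 17% with SD 1). The trial would probably show no clear pain difference either way. This stands and limits the importance of the point.

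Three stronger readings are tempting, and the documents do not support them:
- **That participants who stop drug but stay would corrupt the comparison.** II.D.b mentions stopping together with leaving, and nothing describes staying in follow-up off drug. If some did stay, scoring them in their randomised arm would be a legitimate treatment-policy comparison.
- **That muscle events will go uncompared.** II.K has events assessed at visits and by telephone in all randomised participants, and the safety board reviews safety. V.A is silent on a by-arm table; silence is not a decision to omit one.
- **That the main result is affected.** This argument concerns a secondary outcome and leaves VO2peak untouched.

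**Conclusion.** The point holds as a low-severity, optional improvement. If V.A's baseline-adjusted model is applied to pain and week 12 is the only follow-up rating, early leavers with muscle symptoms contribute nothing, and the difference can be biased toward zero. Under the illustrative assumptions the loss is 0.06 points (0.30 to 0.24) if a quarter of those affected leave and 0.13 (0.30 to 0.17) if half do. The true amount is unknown and may be small; if nobody affected leaves early, nothing is lost. The direction requires only that affected participants leave because of their symptoms and that more are affected on 80 mg. The case for acting is that the change is cheap and an exit rating cannot be obtained afterwards.

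**What to change.** 1. In II.E.a.vi, add the 0-10 pain rating at the existing week-4 visit (blood draw and biopsy) and on the day a participant stops drug or leaves. In V.A, name pain, give its time points as baseline, week 4 and week 12, use the week-4 rating in the mixed model, and report exit ratings by arm.
2. Add to V.A a descriptive by-arm table in all randomised participants, built on the adverse events already assessed under II.K. Count a recorded muscle adverse event, or stopping or leaving for muscle symptoms, regardless of judged relatedness. Give each atorvastatin arm's risk difference against placebo with an exact 95% CI. Blinded staff record the exit reason before referral to the unblinded investigator. Exits for other recorded reasons without a muscle event are non-events; a sensitivity analysis counts unknown reasons as events.
3. Label the week-12 mean as applying to participants with a week-12 rating.

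**Cost.** A few questions per participant, one form field and one table. IV.A already tracks retention and adverse events, but systematic recording of exit reasons is not stated. Sample size and the primary analysis do not change.

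**Limits.** The table has low power, so it sits beside the mean rating and does not replace it. Severity is graded by an unblinded investigator, and grade 3 or above is one route to counting as an adverse event, so the event is not fully protected from knowledge of the arm. Slight soreness that does not alter the intervention remains uncounted in the table. A week-4 rating does not help for symptoms that start later.
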